6.4 Treatment arms

Patients will be assigned to one of the following two treatment arms in a ratio of 1:1 at study visit 1:

- Sacubitril/valsartan at dose levels 1-3 (24mg/26mg, 49mg/51mg and 97mg/103mg BD)
- Valsartan at dose levels 1-3 (40mg, 80mg and 160mg BD)

6.5 Permitted dose adjustments and discontinuation of study treatment

Every attempt should be made to maintain patients at the target study drug dose level throughout the trial. If the patient does not tolerate the target study drug dose level the investigator can, if appropriate, adjust concomitant background medications for co-morbid conditions to rectify the situation, and if necessary down titrate to the next lower study drug dose level. Any dose-adjustment of disease-modifying background therapy, e.g. beta-blockers or MRAs is discouraged.

Down-titration of the study drug at any time will be allowed based on the safety and tolerability criteria defined in Table 4-3 and section 6.8. If down-titration is necessary, the patient should be down-titrated to the next lower dose level (Table 4-2) The patient may continue receiving the lower dose level for a recommended period of 1 to 4 weeks before re-challenging the patient with the next higher dose level. For example, a patient who encounters tolerability problems at the target dose level (dose level 3), should receive the study drug at dose level 2 for 1 to 4 weeks. Then, he/she should be re-challenged with up-titration back to dose level 3. If the tolerability issues are not alleviated despite down-titration by one dose level, the investigator may lower the study drug dose further to the next lower level for 1 to 4 weeks, up to temporary withdrawal of the study drug. Study drug should be reintroduced in those who temporarily discontinue it as soon as medically justified in

the opinion of the investigator. Again, once stable, the patient should be re-challenged with up-titration to the next higher dose level every 1 to 4 weeks in an attempt to bring back the patient gradually to the target study drug dose level (dose level 3). The investigator may choose the next dose level for down- or up-titration according to his or her judgement.

In some instances, according to the safety and tolerability criteria and the investigator's judgment, dose level 1 or 2 could be maintained if he/she considers that the patient's condition would not allow any further up-titration to the target dose of study medication (level 3). In this case it would be acceptable to maintain the patient at dose level 1 or level 2, whichever is the higher and tolerated dose level by the patient.

Any dose change must be recorded on the dosage administration record on the eCRF.

Should a patient develop symptomatic heart failure during the study they will be offered open-label sacubitril/valsartan. Patients starting open-label sacubitril/valsartan or withdrawing from study medication (or study follow-up) ≥ 6 months after randomisation will be asked to undergo an end-of-study CMR examination (patient withdrawing before 6 months will not be asked to have a second CMR as an effect of LV remodelling is unlikely to be detected before this time point).

The emergence of the following circumstances will require permanent study drug discontinuation:

- Withdrawal of informed consent
- Investigator thinks that continuation of study drug would be detrimental to the patient's well-being
- Suspected or confirmed occurrence of clinically significant angioedema. A patient with any signs or symptoms of clinically significant angioedema should be thoroughly evaluated by the investigator
- Pregnancy and post-pregnancy during lactation period

The emergence of the following circumstances will require temporary or permanent discontinuation (study drug may be restarted once these circumstances no longer exist):

- Use of an open label ACE inhibitor, ARB, direct renin inhibitor, lithium, cholestyramine or colestipol resins (*Table 6-1*)
- Any laboratory abnormalities that in the judgment of the investigator warrant discontinuation of study drug after taking into consideration the patient's overall condition

Study drug may be discontinued at the investigator's discretion if any of the following occurs:

- Any severe suspected drug-related AE

- Any other protocol deviation that results in a significant risk to the patient's safety
- Subsequent clinical need for implantable cardiac device insertion (e.g. permanent pacemaker, implantable cardioverter defibrillator, cardiac resynchronisation therapy)

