5.3 Women of child bearing potential

Women of childbearing potential must be currently adhering to, or be willing to use, highly effective birth control methods for study treatment duration and for seven days thereafter including:

- Combined hormonal contraception (oestrogen and progestogen containing medication) either orally, intravaginally, or transdermally
- Progesterone only hormonal contraception either orally, injected, or implanted
- Progesterone only hormonal contraception either orally, injected, or implanted

- Intrauterine device (IUD)
- Intrauterine hormone release system (IUS)
- Bilateral fallopian tube occlusion
- Vasectomised partner
- Complete sexual abstinence where this is their preferred and usual lifestyle

Women of child bearing potential (WOCBP) comprises women who have experienced menarche and who have not undergone successful surgical sterilisation (hysterectomy, bilateral tubal ligation, or bilateral oophorectomy) or who are not post-menopausal defined as:

- Women who have had amenorrhea for \geq 12 consecutive months (without another medical cause) and who have a documented serum follicle-stimulating hormone (FSH) level $>$ 35 mIU/mL.
- Women who have irregular menstrual periods and a documented serum FSH level $>$ 35 mIU/mL.
- Females of childbearing potential must have a negative pregnancy test within 7 days prior to the initiation of treatment.

Pregnancy tests will be performed in WOBCP at the following visits: Visit 1 (week 0), 4 (week 4), 6 (week 14), 7 (week 26), 8 (Week 39), and 9 (week 52). Should this test be positive, then the patient will be immediately withdrawn from the trial and study drug will be discontinued.

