6.8.4 Management of angioedema

Angioedema is a potential side effect of combined RAAS and NEP inhibition. Angioedema has been reported in patients treated with sacubitril/valsartan. If angioedema occurs, study drug should be immediately discontinued and appropriate therapy and monitoring should be provided until complete and sustained resolution of signs and symptoms has occurred. It must not be re-administered. Any patients who experience angioedema during the trial will be withdrawn from the study.

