6.9 Withdrawal of treatment

Any patient enrolled in the trial will be free to withdraw from the study at any time without giving reason and without prejudicing any further treatment/care. Following their involvement in the trial any patient withdrawing will be converted to an ACE-inhibitor or ARB as per local practice guidelines at an equivalent dose to their final study drug dose level.

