8.2.2 CMR protocol

All CMR scans will be performed on a single 3.0 Tesla Siemens MAGNETOM Prisma scanner located in the CRF at the QEUH. The MRI scan will include cine MRI, T1 and T2 maps, strain encoded MRI, and contrast enhanced imaging including first pass perfusion at rest, microvascular obstruction and late gadolinium enhancement imaging 10 - 15 min after contrast administration. IV access will be required for contrast administration and a full blood count will be obtained before the scan in order to measure extracellular volume. Specific details of the CMR protocol are detailed in a local Standard Operating Procedure. Patients will be provided with an MRI information sheet prior to their visit (Appendix 2).

8.3 26-week visit

This will comprise of a half-day visit to the QEUH CRF. A number of the baseline investigations will be repeated:

- full physical examination
- spot urine collection
- venepuncture – 50ml blood withdrawn for biochemical and hormonal analysis

Patients will also be asked to complete a short patient global assessment questionnaire (Appendix 3) at this visit.

8.4 52-week visit (+/- 3 months)

This will comprise of a half-day visit to the QEUH CRF. A number of the baseline investigations will be repeated:

- full physical examination
- spot urine collection
- venepuncture – 50ml blood withdrawn for biochemical and hormonal analysis
- cardiac MRI with gadolinium contrast will be performed.

Patients will also be asked to complete a short patient global assessment (Appendix 3) questionnaire at this visit.

In response to the COVID-19 pandemic we have allowed an extension of the patients IMP treatment by up to 3 months. During this extended time on IMP we would anticipate following up with patients by telephone every 6 weeks. Patients have the clinical research team contact details should they wish to discuss any aspect of the extended involvement themselves.

At this point a patient's participation in the involvement in the trial will end. They will return any unused study drug. Following their involvement in the trial patients will be converted to an ACE-inhibitor or ARB as per local practice guidelines at an equivalent dose to their final study drug dose level. Prior to commencement of any ACE-inhibitor, patients will require to have a 36-hour washout period following their last dose of study drug in order to reduce the risk of angioedema associated with combined ACE and NEP inhibition.

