11.3 Statistical analysis

The study will have a comprehensive Statistical Analysis Plan, which will be authored by the Trial Statistician and agreed by the Investigators before the final unblinded analysis. Analysis will be done on an intention-to-treat basis. The Robertson Centre for Biostatistics, functional unit of the Glasgow Clinical Trials Unit, a fully registered UK CRN Clinical Trials Unit, will manage and analyse trial data.

The primary analysis will compare LVESVI at 12 months between randomised groups using a linear regression model, adjusted for baseline LVESVI, and whether or not taking diuretics at baseline. Similar methods will be applied to secondary outcomes. Safety data will be summarised without formal statistical comparison.

12 Data handling

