2.1. STUDY POPULATION

The analysis population will comprise of all subjects randomised into the study.

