2.4. EFFICACY OUTCOMES

2.4.1. PRIMARY OUTCOME

The change in indexed left ventricular end-systolic volume (LVESVI) from baseline to the 12 month follow-up visit will be summarised overall and by randomised group and compared between randomised groups using a linear regression model adjusted for baseline LVESVI, diuretic use at baseline and time from baseline to the 12 month follow-up visit.

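### Patients who stop study drug before 6 months are not asked for the primary-outcome CMR, although the analysis is stated to be intention-to-treat

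*Protocol*

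**What the plan says.** Protocol 6.5 deals in one sentence with patients who start open-label sacubitril/valsartan, patients who withdraw from study medication and patients who withdraw from follow-up. If this happens at 6 months or later, they are asked for an end-of-study CMR. The parenthesis that follows says: "patient withdrawing before 6 months will not be asked to have a second CMR". The reason given is that a remodelling effect is unlikely to be detectable that early.

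The schedule of assessments (Protocol Table 9-1) has CMR at Visit 1 and Visit 9 only. Protocol 8.4 says of the 52-week visit that "cardiac MRI with gadolinium contrast will be performed", with no exception for early stoppers.

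On analysis, Protocol 11.3 says "Analysis will be done on an intention-to-treat basis" and SAP 2.1 says "The analysis population will comprise of all subjects randomised into the study". Under SAP 2.4.1 the change in LVESVI is "compared between randomised groups using a linear regression model adjusted for baseline LVESVI", diuretic use and time to the follow-up visit. Neither document gives a method or a sensitivity analysis for a missing 12-month CMR.

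Two other sections tie a drug-stopping event to leaving the study. After a positive pregnancy test (Protocol 5.3), "the patient will be immediately withdrawn from the trial and study drug will be discontinued". Protocol 6.8.4 says: "Any patients who experience angioedema during the trial will be withdrawn from the study".

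**The concern.** Stopping a drug and leaving a trial are different events, and SAP 2.2 counts them separately. Protocol 6.5 gives them the same consequence for the primary outcome. A patient who stops tablets at month 3 and would gladly return at month 12 is not asked for the scan.

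The stated reason is an argument against scanning at the moment of early withdrawal. It is no argument against the scheduled 52-week scan, when that patient is as far from randomisation as everyone else.

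A regression on LVESVI change can use only patients with two scans. Without a missing-data method, the primary analysis becomes a complete-case comparison, partly conditional on staying on drug to 6 months. Early permanent stopping can follow hypotension, renal decline, hyperkalaemia or angioedema, and these may differ between arms. The same sentence also appears to leave out patients who start open-label sacubitril/valsartan for heart failure before 6 months, and that missingness is related to the outcome. Measurements never taken cannot be fully recovered by later analysis.

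**Working it through.** **Inputs from the documents** (Protocol 11.1, repeated in SAP 1.5): 45 patients per group, difference 6 mL/m², SD 7.8 mL/m², alpha 0.05 (taken as two-sided; the documents do not say), 10% discontinuation, total 100.

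**Assumed inputs.** The documents give neither an early-withdrawal rate by arm nor the outcome of unscanned patients. The proportion unscanned, p, is varied from 5% to 20%. The gap, g, is the difference in mean LVESVI change between unscanned and scanned patients of the same arm. It is set at 6 (the whole target effect) or 7.8 (one SD).

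**The plan's own figure.** SE = 7.8 × √(1/45 + 1/45) = 1.644, and 6/1.644 = 3.65. Power from the noncentral t with 88 df is 95.0%, which agrees with the stated figure of more than 90%. Also 90/0.9 = 100. Loss of power is not the difficulty: with 20% unscanned (40 per arm), power is still 92.5%.

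**Bias.** In each arm, the mean over all randomised patients equals the scanned mean plus p × g. The scanned-only difference therefore departs from the all-randomised difference by pA·gA − pB·gB.

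| Unscanned, arm A / arm B | Gap, arm A / arm B | Bias (mL/m²) | Share of 6 mL/m² |
|---|---|---|---|
| 10% / 10% | 6 / 6 | 0 | 0% |
| 5% / 5% | 6 / 0 | 0.30 | 5% |
| 5% / 5% | 7.8 / 0 | 0.39 | 6.5% |
| 10% / 10% | 6 / 0 | 0.60 | 10% |
| 10% / 10% | 7.8 / 0 | 0.78 | 13% |
| 15% / 5% | 6 / 6 | 0.60 | 10% |
| 15% / 5% | 7.8 / 7.8 | 0.78 | 13% |
| 20% / 5% | 7.8 / 7.8 | 1.17 | 19.5% |

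The direction depends on which arm loses the worse patients.

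**Type I error,** if the gap is prognostic and the drug has no effect:
- 10% unscanned (45 per arm, SE 1.644): bias/SE is 0.60/1.644 = 0.36 or 0.78/1.644 = 0.47. The two-sided error is 6.5% or 7.6%.
- 5% unscanned (47.5 per arm, SE = 7.8 × √(2/47.5) = 1.601): bias/SE is 0.19 or 0.24. The error is 5.4% or 5.7%.
- If the gap is nothing but lost drug effect, it vanishes when the drug has no effect, and type I error is not inflated.

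**Power if early stoppers are scanned.** Take 50 per arm, with a fraction s of the sacubitril/valsartan arm keeping no effect, so that the difference is 6 × (1 − s). The second power figure in each line adds the mixture variance s(1 − s) × 36 to that arm.
- s = 10%: difference 5.4, power 92.9%, or 92.3% with added variance 3.24.
- s = 15%: difference 5.1, power 89.9%, or 88.8% with added variance 4.59.

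**The case against.** The affected group may be very small. Most intolerance is handled by dose reduction, temporary interruption and rechallenge (Protocol 6.5), and those patients stay in, as do patients who withdraw at 6 months or later. All entrants already tolerate an ACE inhibitor or ARB. Several sections treat stopping as leaving: 5.3, 6.8.4, and 6.9, where "any patient withdrawing will be converted to an ACE-inhibitor or ARB as per local practice guidelines". No section describes a patient who stops early and still attends week 52. Not being asked is also not a prohibition. This limits the number affected, which is unknown, but the wording of 6.5 still reaches drug-only stoppers.

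An all-randomised population with some missing outcomes is common and is not by itself a contradiction. That is fair. The difference here is that the outcome is left uncollected by rule in patients who may be willing.

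The bias figures are assumptions, and gaps of 6 or 7.8 are large. The model adjusts for baseline LVESVI, diuretics and time, so only a gap that remains after adjustment matters. The 10% allowance also includes deaths and true losses, so this rule's share is lower. These points stand, and the larger figures should be read as upper guides.

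The power figures for the change assume that all 100 patients are scanned. With 45 scanned per arm, they fall to 89–90% at 10% stopping and 85–87% at 15%. The arithmetic is right, but it needs 10% unscanned plus a further 10–15% early stoppers, which exceeds the plan's total allowance of 10%.

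The SAP is at version 1.1 and cites a protocol of August 2020, so many early stoppers may be past recall. A fallback is therefore needed.

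**Conclusion.** The point holds. As written, Protocol 6.5 leaves willing patients who stop study drug before 6 months without a primary outcome. Its stated reason does not justify omitting the week-52 scan, and the analysis plan has nothing to put in its place.

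The likely size is modest. Bias is zero if stopping rates and outcome gaps match across arms. It is 0.30 to 0.78 mL/m² under the 5% to 10% assumptions, against an SE of about 1.6, and exceeds 1 mL/m² only in the strongly unequal case of 20% versus 5%. All of this rests on assumed rates and gaps. The 10% allowance in Protocol 11.1 protects power; it does not protect against selective missingness. The matter should be corrected, but it does not undermine the trial as a whole. Confidence is medium, because the number of patients affected is not known.

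**What to change.** **If patients are still in follow-up.** Amend Protocol 6.5 so that every randomised patient who stops study drug before 6 months, and who still consents to and is able to undergo CMR, is asked to attend the scheduled 52-week CMR and blood sampling. Except patients with a new contraindication to CMR, such as an implanted device, and those who are pregnant (Protocol 5.2). State in SAP 2.4.1 that these scans enter the primary model under the randomised arm. Reconcile Protocol 5.3 and 6.8.4 with this, so that stopping drug does not by itself end outcome follow-up. No change to when study drug is stopped is proposed.

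**If follow-up is complete,** then before unblinding:
- Describe the primary analysis as one of patients with a second CMR.
- Report missing CMRs by arm and reason. SAP 2.2 already counts withdrawal from medication and from follow-up separately.
- Add a delta-adjusted multiple-imputation sensitivity analysis using baseline LVESVI, the randomisation strata and arm, with 26-week biomarkers only where available.

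**Cost.** The change needs wording in three protocol sections and a short SAP addition. The 52-week CMR is already planned for all 100 patients, so a few off-drug patients would attend one visit that was planned anyway. Including them may dilute the effect slightly: power is about 92–93% at 10% early stopping and 89–90% at 15% if all 100 are scanned, against 95% for the planned 45 per arm with the full effect.

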6.6 Concomitant medications

Prior to randomisation and at each study visit a list of the patient's current medications will be reviewed and the patient will be instructed to inform the investigator about any new medications he/she takes after enrolment in the study. Each new medication must be individually assessed against the exclusion criteria and list of prohibited medication below (*Table 6-1*)

Medications known to raise potassium levels

Potassium-sparing diuretics, potassium supplements and any other medications known to raise potassium levels should be used with caution while the patient is receiving the study drug due to the increased possibility of occurrence of hyperkalemia. Patient's potassium levels will be monitored regularly, especially in those who are receiving these medications.

Phosphodiesterase-5 (PDE-5) inhibitors

PDE-5 inhibitors should be used with caution while the patient is receiving study medication due to the increased possibility of the occurrence of hypotension.

HMG-CoA reductase inhibitors (statins)

Caution is recommended when co-administering sacubitril/valsartan with atorvastatin or other statins because of the potential to raise its plasma level.

Non-steroidal anti-inflammatory drugs (NSAIDs)

In elderly patients, volume-depleted patients (including those on diuretic therapy), or patients with compromised renal function, concomitant use of sacubitril/valsartan or valsartan and NSAIDs may lead to an increased risk of worsening of renal function. Close monitoring of renal function as per study protocol will take place in all patients.

OATP and MRP2 transporters

The active metabolite of sacubitril (LBQ657) and valsartan are OATP1B1, OATP1B3, OAT1 and OAT3 substrates; valsartan is also a MRP2 substrate. Therefore, co-administration of Entresto with inhibitors of OATP1B1, OATP1B3, OAT3 (e.g. rifampicin, ciclosporin), OAT1 (e.g. tenofovir, cidofovir) or MRP2 (e.g. ritonavir) may increase the systemic exposure of LBQ657 or valsartan. Appropriate care should be exercised when initiating or ending concomitant treatment with such medicinal products.

Prohibited medication

Use of the treatments displayed in *Table 6-1* is NOT allowed after the start of study drug due to safety reasons, unless the actions specified are taken.

Table 6-1 Prohibited medications

Medication	Action taken
Any ACE inhibitor	Discontinue study drug. The open label ACE inhibitor must be stopped for ≥ 36 hours prior to re-initiation of study drug
Any ARB	Discontinue study drug. The open label ARB must be stopped prior to re-initiation of study drug
Any direct renin inhibitor	Discontinue study drug. The open label direct renin inhibitor must be stopped prior to re-initiation of study drug
Entresto (commercially available sacubitril/valsartan)	Discontinue study drug. The open label Entresto must be stopped for ≥ 36 hours prior to re-initiation of study drug
Lithium	Discontinue study drug. Lithium must be stopped prior to re-initiation of study drug
Cholestyramine or colestipol resins	Discontinue study drug. Cholestyramine or colestipol resins must be stopped prior to re-initiation of study drug

The concomitant use of open-label ACE inhibitor, ARBs, commercially available sacubitril/valsartan (Entresto) or a direct renin inhibitor is **strictly prohibited** while the patient is receiving study drug. If the addition of an ACE inhibitor, ARB, Entresto or direct renin inhibitor is necessary, then study drug must be temporarily discontinued. If the patient is to be started on open-label ACE inhibitor or Entresto, the study drug must be stopped ≥ 36 hours prior to initiating ACE inhibitor or Entresto. If study drug is to be re-started, the open-label ACE inhibitor or Entresto must also be stopped ≥ 36 hours prior to re-initiating study drug. ARBs or a direct renin inhibitor should be stopped prior to resuming study drug.

